**8.1.2. Drug Concentration Measures**

Concentrations of plasma GSK3008356 will be listed by Part, Treatment Subject, Day and time, and summarised by Part, Treatment, Day and nominal time for the active treatment groups. Standard summary statistics will be calculated (i.e. n, mean, standard deviation, median, minimum and maximum).

Trough plasma concentration (Ctrough) collected at pre-dose on Days 2, 4, 5, 6, 12, 13, 14 together with the 24h post-dose on Day 14 from Part 2 will be listed, and summarized by Active Treatment and Day.

Individual plasma concentration-time profiles and median/mean profiles by treatment group (i.e., by Part, and then Treatment) will be plotted for Part 1 and Part 2 at Day 1 and Day 1 and Day 14 respectively. Each of the figures will contain one plot on the untransformed scale (i.e. a linear plot) and one plot on the log transformed scale (i.e. semi log plot).

**8.1.3. Pharmacokinetic Parameters**

**8.1.3.1. Deriving Pharmacokinetic Parameters**

Deriving Pharmacokinetic Parameters:

- Refer to [Appendix 5: Data Display Standards & Handling Conventions \(Section 11.5.3 Reporting Process & Standards\)](#).

- The pharmacokinetic parameters will be calculated by standard non-compartmental analysis according to current working practices and using Phoenix WinNonlin Version 6.2.1 or higher.
- All calculations of non-compartmental parameters will be based on actual sampling times.
- Pharmacokinetic parameters described in [Table 7](#) will be determined from the plasma concentration-time data, as data permits.

**Table 7 Derived Pharmacokinetic Parameters**

Parameter	Parameter Description
AUC (0-t) (Part 1)	Area under the concentration-time curve from time zero to the time of the last quantifiable concentration (C(t)) will be calculated using the linear trapezoidal rule for each incremental trapezoid and the log trapezoidal rule for each decremental trapezoid.
AUC (0-τ) (Part 2)	Area under the concentration-time curve from time zero to the time of the end of dosing interval (C(T)) will be calculated using the linear trapezoidal rule for each incremental trapezoid and the log trapezoidal rule for each decremental trapezoid.
AUC (0-24) (Part 1)	Area under the concentration-time curve from time zero to the time of the 24 hour concentration (C(24h)) will be calculated using the linear trapezoidal rule for each incremental trapezoid and the log trapezoidal rule for each decremental trapezoid.
AUC 0-∞ (Part 1 + Part 2 day 1)	Area under the concentration-time curve extrapolated to infinity will be calculated as: AUC(0-inf) = AUC(0-t) + C(t) / lambdaz This parameter will only be calculated for the single-dose profiles in Part 1 and Day 1 in Part 2.
C max	Maximum observed concentration, determined directly from the concentration-time data.
C t	Last quantified observed concentration, determined directly from the concentration-time data.
T max	Time to reach C max , determined directly from the concentration-time data.
t 1/2	Apparent terminal half-life will be calculated as: t1/2 = ln2 / lambdaz
A e	Cumulative amount of drug excreted in urine. $A_e = \sum C_{ur} * V_{ur}$ Where C ur is the concentration in urine and V ur is the volume of urine
CL r	Renal Clearance [1] Single Dose: CL r = A e /AUC inf [2] Repeat Dose: CL r = A e τ /AUC τ Where A e τ is cumulative amount of drug excreted in urine over a dosing interval.
C trough (Part 2)	Observed Concentration at the end of a dosing interval, immediately before next administration. Directly obtained from the observed concentration vs. time curves. They are the pre-dose concentration on Days 2, 4, 5, 6, 12, 13, 14 and the 24 h post dose on Day 14.
R 0 (Part 2)	Accumulation Ratio, calculated in the multi-dose regimens, as the ratio [AUC 0-τ on the final day (Day 14)]/[AUC 0-τ on Day 1]

Parameter	Parameter Description
R cm (Part 2)	Accumulation Ratio, calculated in the multi-dose regimens, as the ratio [C max on the final day (Day 14)]/[C max on Day 1]
R s (Part 2)	Steady-state Accumulation Ratio, calculated in the multi-dose regimens, as the ratio [AUC(0-tau) on final day (Day 14)]/[ AUC 0-∞ on Day 1]

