Specifically, **Part 1** doses with PD activity would be progressed into **Part 2**. GI tolerability was not expected to be an issue in **Part 1** and not expected to impact progression into **Part 2**. **Part 2** doses with PD activity and which had tolerability from a GI AE perspective were to be progressed into **Part 3**.

**Part 1** data indicated that single doses of 125 mg or greater were tolerated and had postprandial TG suppression. Divided doses of 45 mg GSK3008356 or greater were tolerated and had postprandial TG suppression. The dose of 45 mg (5 mg hourly for 9 hours) had complete suppression. Divided doses below 45 mg GSK3008356 were not evaluated and exploration of lower divided doses was planned for **Part 2**.

Based on **Part 1** data, the short observed GSK3008356 half-life and future NOAEL identified from a 13 week repeat dose dog toxicology study, **Part 2** initially evaluated placebo or 20 mg GSK3008356 as 10 mg at time 0h and 16h.

Blinded data indicate that 20 mg GSK3008356 divided dosing was not tolerated with 6 of 8 subjects withdrawn early due to GI issues. Dosing was stopped for all subjects before Day 7 of a planned 14 days: 6 due to the GI issues and 2 as the remaining subjects in the cohort were discontinued following discussions between GSK and the Principle Investigator. No PD (postprandial TG suppression) was observed on Day 1; Day 14 could not be evaluated.

Subsequently, placebo or 2 mg GSK3008356 as 1 mg at time 0h and 16h and placebo or 6 mg GSK3008356 as 3 mg at time 0h and 16h were evaluated in Cohorts 2 and 3. All subjects except for 1 in the placebo or 6mg cohort completed the 14 days of dosing, indicating that the doses were tolerated. However, no postprandial TG suppression was observed in either the 2mg or 6mg GSK3008356 divided dosing cohorts.

Based on these data, **Part 2** did not identify a tolerated dose with PD activity and **Part 3** was not initiated.

[figure not shown]
For the purposes of the 204856 RAP, all sections and references pertaining to **Part 3** will be redacted. For any information pertaining to **Part 3** design, objectives and endpoints, please refer to the relevant sections in the protocol. Analysis for **Part 3** is therefore not included in the RAP.

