**Accumulation Ratio in Part 2**

Planned Statistical Analyses
Endpoint(s)

 
AUC(0-tau) and Cmax on Day 14 and Day 1 in Part 2;
 

Model Specification

 
The Mixed Model for Ro and Rcmx can be described below: Endpoint = treatment + day + treatment*day + subject (treatment) + random error
 
 
Where endpoint is the loge-transformation of AUC(0-tau) and Cmax. Fixed effects: treatment, day, and treatment*day interaction Random effect: subject within treatment. Treatments will be ordered according to Appendix 5.
 
For accumulation ratio based on parameters in the endpoint(s) above, following loge-transformation, endpoints will be analyzed using a mixed model, fitting fixed effect terms and random effect as specified above. The accumulation ratio of GSK300836 will be estimated by calculating the ratios of AUC(0-tau) and Cmax on Day 14 to Day 1 and the corresponding 90% CI for each cohort in Part 2.
 
An example of the SAS code that will be used for this analysis: Part 2: Proc Mixed;     class treatment day subjid;     model logPKparm = treatment day treatment*day/ s ddfm=kr cl alpha=0.1         outp=pred;     random subjid (treatment) / type = un; run;
 
Note: PKparm is PK parameters: AUC(0-tau) and Cmax on Day 1 and Day 14 in Part 2.

Model Checking

 
Refer to Appendix 10: Model Checking and Diagnostics for Statistical Analyses.
 

Model Results Presentation

 
Point estimates of accumulation ratio with associated 90% CIs will be presented.
 

## Steady State Assessment in Part 2

Planned Statistical Analyses
Endpoint(s)

 
• <math>C_{\text{trough}}</math> in Part 2
 

Model Specification

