
1. Day 1 and 14 only. For cohorts where multiple doses are to be administered either q1h or q16h, Time 0 is the first dose and subsequent doses are per regimen (q1h or q16) and the subsequent doses are not noted on the T&E Table.
 
2. PK Samples included in table to provide relative time to dosing, fat meal and triglyceride assessment. The full PK time points are found in Section 11.2.1.3, Section 11.2.1.4, and Section 11.2.1.5.
																

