**NOTES :**

- Any actual draws outside of these time windows will be listed as deviations (not necessarily “important”), but will still be used in the concentration assay and determination of PK parameters according to the actual draw time.
- Any concentrations determined from blood draws inside or outside these windows may still be excluded from PK determinations for other reasons, such as sample handling or other protocol deviations.
- \* All Subsequent draws after 2 hour will be at hours 4, 6, 8, 12, 18, 24, 36, 48, and 72 in Part 1.
- In Part 2, All Subsequent draws after 2 hour will be at hours 4, 6, 8, 12, and 18 on Day 1; then PK Samples will be taken at Pre-Dose on Days 2, 4, 5, 6, 12, and 13 only during period Days 2-13 Morning Dose; and starting on Day 14, PK Samples will be taken at Pre-dose, hours at 0.25, 0.5, 1, 1.5, 2, 4, 6, 8, 12, 18, 24, 36, 48, and 72.

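### Part 2 AUC(0-tau) spans the 16h dose on one straight line from 12h to 18h, so its level is off by roughly -16% to +11% or more; tau should be stated and AUC(0-12) reported beside it

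*SAP*

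**What the plan says.** **Dosing.** SAP section 2.2 reports that Part 2 used two doses a day: 10 mg twice in Cohort 1, then "placebo or 2 mg GSK3008356 as 1 mg at time 0h and 16h", then 3 mg on the same schedule.

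**Sampling.** SAP section 11.3.1: "In Part 2, All Subsequent draws after 2 hour will be at hours 4, 6, 8, 12, and 18 on Day 1", with the 24h value taken as the Day 2 pre-dose sample. Day 14 is sampled pre-dose and at "hours at 0.25, 0.5, 1, 1.5, 2, 4, 6, 8, 12, 18, 24, 36, 48, and 72". Neither day has a draw between 12h and 18h. The 16h dose does not appear in the schedule; the footnote says "subsequent doses are per regimen (q1h or q16) and the subsequent doses are not noted on the T&E Table".

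**Derivation.** SAP Table 7 takes AUC(0-tau) "from time zero to the time of the end of dosing interval (C(T)) will be calculated using the linear trapezoidal rule" where concentrations rise, and by the log version where they fall.

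**Tau.** No value in hours is given. Table 7 defines trough values as end-of-interval concentrations: "They are the pre-dose concentration on Days 2, 4, 5, 6, 12, 13, 14 and the 24 h post dose on Day 14". That implies 24h, although SAP section 11.5.1 calls every Part 2 regimen BID.

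**Use.** AUC(0-tau) on Days 1 and 14 is a secondary PK endpoint. It enters the Part 2 power model, and "The accumulation ratio of GSK300836 will be estimated by calculating the ratios of AUC(0-tau) and Cmax on Day 14 to Day 1".

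**The concern.** Between 12h and 18h the concentration falls to a trough, a dose is given, and absorption begins. The plan describes this with two points: one near the trough and one 2h after the dose. Because the 18h value is the higher, the rule joins them linearly. The line can overstate the area, since it rises through four hours in which no new drug was present. It can also understate it, if the true peak came and went before 18h.

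The stake is a reported exposure level for half the daily dose. It also matters whether that error passes into R0 and the dose-proportionality slope.

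**Working it through.** The documents give no figure for AUC error, so there is nothing to reproduce. The check simulates the regimen and applies the SAP rule.

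**Inputs from the documents**
- Doses at 0h and 16h (SAP 2.2). Draws at 0, 0.25, 0.5, 1, 1.5, 2, 4, 6, 8, 12, 18 and 24h (SAP 11.2.1.3 to 11.3.1).
- Observed half-life 1.5 to 3h (protocol 3.1.1).
- Observed 10 mg exposure: Cmax 191 ng/mL and AUC(0-inf) 314 ng.h/mL (protocol Table 5), so AUC/Cmax = 314/191 = 1.64h.
- Six active subjects per cohort (SAP 2.4).

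**Assumed, because the documents do not give them:** absorption rate ka (0.7 to 8 per h), any lag, and their within-subject variability.

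**Models.** (a) One compartment, half-life 1.5 to 3h, ka 0.7 to 6 per h. (b) Biexponential, terminal half-life 1.5 to 3h, calibrated to AUC/Cmax = 1.64h. Doses are superposed over 14 days.

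**Step 1: one example by hand.** Model (a), half-life 2h, ka = 1.4, unit dose and volume. ke = ln2/2 = 0.3466 and C(t) = ka/(ka - ke) x [exp(-ke t) - exp(-ka t)] for each dose. Then C(12) = 0.0208 and C(18) = 0.5863.
- SAP rule, 12-18h: 6 x (0.0208 + 0.5863)/2 = 1.821. True area: 1.078. Error +69%.
- AUC(0-24): 6.156 against a true 5.530, or +11.3%.

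A calibrated model (b) with a 3h terminal half-life errs the other way. The 12-18h segment is 0.384 against 0.718 (-46%), and the total is 1.655 against 1.931 (-14.3%).

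**Step 2: results over the model grid**

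| Quantity | Result |
|---|---|
| AUC(0-24) error, no lag, model (a) | +0.6% to +11% |
| AUC(0-24) error, no lag, model (b) | -11% to -16% |
| AUC(0-24) error, second dose 0.5 to 1h late | mostly +9% to +49% (extremes -4% and +50%) |
| True R0 | 1.003 to 1.136 |
| R0 bias, no lag | about 1% or less |
| R0 bias, 1h lag on both days | up to about 2% |
| AUC(0-12) error | -0.7% to -2.8% |

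In the hand example, R0 is 1.044 true and 1.039 by the SAP rule. The AUC(0-12) ratio is 1.084 true and 1.085 estimated. AUC(0-12) shows about twice the signal because, on Day 14, it carries over drug from a dose given only 8h before.

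**Step 3: noise in R0.** With ka and lag redrawn for each dose (SD of log ka 0.3 to 0.5; lag 0 to 0.5h or 0 to 1h), the per-subject SD of the log R0 error is 0.02 to 0.22. With n = 6, the 90% half-width is 2.015 x SD/sqrt(6) on the log scale, or about 2% to 20% from this source alone. As a single-subject illustration in model (b), a 0.5h lag on Day 1 and none on Day 14 gives an estimated R0 of 0.81 to 0.94 against a true 1.01 to 1.06.

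**Step 4: dose-proportionality slope.** If the percentage error is the same at every dose, it moves only the intercept and slope bias is 0. In a worst case, with +11% at one end of the dose range and -16% at the other, the bias is ln(1.11/0.84)/ln(10) = 0.12 over 1 to 10 mg, or ln(1.11/0.84)/ln(3) = 0.25 over 1 to 3 mg. Cmax/AUC in protocol Table 5 runs from 0.34 to 0.61 per h across 5 to 200 mg, so constant shape is not assured. Only 5 and 10 mg (0.48 and 0.61) lie in the Part 2 per-dose range.

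**The case against.** The strongest reply is that R0 is a within-subject ratio on an identical schedule, so the trapezoid error divides out. That stands: systematic bias is about 1% and never exceeds the true accumulation in the no-lag models. The second dose is also not unsampled, since 18h and 24h lie 2h and 8h after it.

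A reader might infer that the error swamps any accumulation the study could detect. The documents do not support this. With the originally predicted 14.1h half-life, true R0 would be 2.03 and the SAP rule would return 1.98. Large shifts in R0 require second-dose absorption to differ between Day 1 and Day 14, and the documents give no lag or absorption variability. Random shifts widen the interval; they bias the cohort estimate only if most subjects shift the same way.

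Precision is limited in any case. An assumed within-subject CV of 10% to 30% at n = 6 gives a 90% CI of x/÷ 1.12 to 1.41 even with full sampling. R0 is available only for Cohorts 2 and 3, because Cohort 1 stopped before Day 7. The endpoint is secondary and estimation-only.

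Two tempting remedies also fail. Doubling the first-dose AUC assumes that the second dose behaves like the first. Moving the draws is moot, because Part 2 is complete and Part 3 was not started.

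What remains is the misstated AUC(0-tau) level and a source of noise that existing data can avoid.

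**Conclusion.** The concern holds for the level of AUC(0-tau) and only in part for what is built on it. With tau = 24h, following Table 7 misstates a reported secondary endpoint by roughly -16% to +11% with prompt absorption, and usually by more if the second dose is absorbed late. The delayed figures rest on assumed lags.

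R0 is nearly unbiased but noisier than it need be. Whether that noise matches the expected accumulation of 0.3% to 14% depends on absorption variability the documents do not report. The dose-proportionality slope is safe if profile shape is constant across doses and otherwise exposed.

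One further dependence: neither the quantification limit nor the rule for unquantifiable values in the AUC calculation is stated. If the 12h value were dropped on Day 1 only, estimated R0 would fall to about 0.82 to 0.92 in the models tried.

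**What to change.** In SAP Table 7 and section 8.1.3.2:

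1. State tau in hours.
2. Add AUC(0-12) on Days 1 and 14 as a pre-specified partial area.
3. Report Part 2 R0 and dose proportionality on AUC(0-12) alongside the protocol-defined AUC(0-tau), which stays.
4. Footnote AUC(0-tau) as approximate because of the 12-18h gap.
5. State that C(16h) will not be interpolated using the 18h value, because that would put second-dose drug into the first interval.

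The cost is SAP wording and one re-run of the partial areas; the notes to Table 7 already allow extra parameters. The drawback is that AUC(0-12) says nothing about the second daily dose, which is why it belongs beside AUC(0-tau) and not in its place.

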3. STUDY DESIGN

3.1. Overall Design

Study 204856 will be a randomized, double-blind (sponsor unblind), placebo controlled trial in three Parts.

1. Part 1, will be a single-dose (SD), dose-rising study in healthy subjects. Subjects will receive GSK3008356 (or matching placebo), as a single dose in each of five sequential cohorts while receiving a standard 30% fat meal. The initial dosing for the first cohort will be staggered so that 2 subjects will be dosed as sentinel subjects. Provided there are no safety concerns, the remainder of the subjects scheduled for the cohort may be dosed.

2. Part 2, will be a 14-day, repeat-dose (RD), dose-rising study in healthy subjects. Subjects will receive GSK3008356 (or matching placebo), as 14 daily doses in each of three sequential cohorts. Day 1 and day 14 dosing for the first cohort will occur while receiving a standard 30% fat meal. The final two cohorts will receive the same morning 30% fat meals, but will explore daily dosing in the evening rather than in the morning.
3. Part 3, will be a 28-day, repeat-dose study in obese subjects. Subjects will receive GSK3008356 (or matching placebo), as 28 daily doses in each of three parallel cohorts. Cohort 1 will evaluate 1 dose strength of GSK3008356 (or matching placebo) administered as morning doses. Cohorts 2 and 3 will evaluate 2 dose strengths (1 per cohort) of GSK3008356 (or matching placebo) administered in the evening.

Please refer to [Figure 1](#) for details.

Figure 1 Study Part Schematic

Part 1 - SD

[figure not shown]
Part 1 – additional cohorts

Part 2 – RD (14d)

Part 3 – RD (28d)

3.1.1. Additional Cohorts for Part 1

Based on emerging PK data, the original planned Part 1 doses were adjusted, per protocol, to 5, 10, 30, 75 and 200 mg (Section 5.3, Figure 1). This was due to a much shorter observed half-life compared to the predicted half-life (1.5-3h observed versus 14.1h predicted).

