10. For cohorts where multiple doses are to be administered either q1h, q4h or q16h, Time 0 is the first dose and subsequent doses are per regimen (q1h, q4h or q16) and the subsequent doses are not noted on the T&E Table. For the single evening cohort, the dose will be at hour 16 and not noted on the T&E Table.

6.1.1.1. Part 1, Single Dose, Fat Meal Challenge and Triglyceride Assessment Relative to Dose and PK Sampling

	Day -1, Day 1															
	Pre-dose	0h	0.25h	0.5h	1h	1.5h	2h	3h	4h	5h	6h	7h	8h	9h	12h	18h
Study Drug Dose ^{1,3}		X ³														
Fat Meal							X									
Triglyceride Assessment					X		X	X	X	X	X	X	X	X	X	
Plasma Pharmacokinetic Sampling ^{1,2}	X		X	X	X	X	X		X		X		X		X	X

1. Day 1 only
2. PK Samples included in table to provide relative time to dosing, fat meal and triglyceride assessment.
The full PK time points are found in Section 6.1.1
3. For cohorts where multiple doses are to be administered either q1h, q4h or q16h, Time 0 is the first dose and subsequent doses are per regimen (q1h, q4h or q16) and the subsequent doses are not noted on the T&E Table. For the single evening cohort, the dose will be at hour 16 and not noted on the T&E Table

6.1.2. Part 2 – Repeat Dose, Morning Dose Administration, Screening, Day -1, Day 1

	Screening (within 28d)	Day -2, Day -1 ⁹	Day 1													
			Pre-dose	0h	0.25h	0.5h	1h	1.5h	2h	4h	6h	8h	12h	18h	24h	
Informed Consent	X															
Medical/medication/drug/alcohol history	X	X														
Complete Physical Exam, Weight	X	X ¹														
HIV, Hep B, Hep C	X															
Pregnancy Test ²	X	X														
Estradiol/FSH ³	X															
Urine Drug, Cotinine & Alcohol Screen ⁴	X	X														
Fat Meal ⁵		X							X							
Triglyceride Assessment ⁵		←→					X	←=====→								
Study Drug Dose ¹⁰				X ¹⁰												
Vital Signs (BP, HR, pulse, Temp) ⁶	X	X	X				X				X			X		X
12-Lead ECG	X		X				X				X			X		X
Telemetry			←=====→													
Hematology, Chemistry	X	X										X				X
UA	X	X														X
Exploratory PD Labs	X		X													X
Plasma PK and Metabolite Sampling ^{5,7}			X		X	X	X	X	X	X	X	X	X	X	X	X
Adverse Event Review			←=====→													
BSFS ⁸			←=====→													
Concomitant Medication Review			←=====→													
Outpatient Visits	X															
Inpatient Check-in		X														

1. Brief physical exam, weight.
2. Serum hCG at screening and follow up, urine hCG pre-dose on Day -1 – all females.
3. If indicated.
4. An alcohol breath test is acceptable.

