**11.2. Appendix 2: Time & Events**

**11.2.1. Protocol Defined Time & Events**

**11.2.1.1. Part 1 – Single Dose**

	Screening (within 28d)	Day -2, Day -1 	Day 1													Day 2	Day 3	Day 4	Follow Up (Day 6-8)
			Pre-dose	0h	0.25h	0.5h	1h	1.5h	2h	4h	6h	8h	12h	18h	24h				
Informed Consent	X																		
Medical/medication/drug/alcohol history	X	X																	X
Complete Physical Exam, Weight	X	X 																X 	X
HIV, Hep B, Hep C	X																		
Pregnancy Test 	X	X																	X
Estradiol/FSH 	X																		
Urine Drug, Cotinine & Alcohol Screen 	X	X																	
Fat Meal 		X							X										
Triglyceride Assessment 		←→					X		←-----→										
Study Drug Dose 				X 															
Vital Signs (BP, HR, pulse, Temp) 	X	X	X				X			X			X		X		X	X	X
12-Lead ECG	X		X				X			X			X		X			X	
Telemetry			←-----→																
Hematology, Chemistry	X	X													X		X	X	X
UA	X	X													X			X	X
Exploratory PD Labs	X		X												X			X	X
Plasma PK and Metabolite Sampling 			X		X	X	X	X	X	X	X	X	X	X	X	X	X	X	
Urine PK and Metabolite Sampling 			←→	←-----→											←→				
Adverse Event Review			←-----→																

	Screening (within 28d)	Day -2, Day -1 	Day 1														Day 2	Day 3	Day 4	Follow Up (Day 6-8)
			Pre-dose	0h	0.25h	0.5h	1h	1.5h	2h	4h	6h	8h	12h	18h	24h	36h	48h	72h		
BSFS 			←=====→																	
Concomitant Medication Review			←=====→																	
Outpatient Visits	X																			X
Inpatient Check-in		X																		
Inpatient Check-out																				X

- Brief physical exam, weight.
- Serum hCG at screening and follow up, urine hCG pre-dose on Day -1 – all females.
- If indicated.
- An alcohol breath test is acceptable.
- Detailed Fat Meal and Triglyceride Assessment relative to Dose and Plasma PK Sampling can be found in Section 6.1.1.1 in Protocol Amendment 2.
- Temperature Screening and Day -1 only.
- Plasma analysis for circulating metabolite profile; Urine analysis to aid structural identification. Urine samples for parent and metabolite structure will be collected pre-dose and over the post-dose intervals 0-12 hours and 12-24 hours. Plasma and urine samples for metabolites will be analyzed from only the highest dose cohort.

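### Part 1 renal clearance divides urine collected to 24 h by AUC to infinity; the mismatch is negligible for single doses and matters only for the 0h/16h cohort

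*SAP*

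**What the plan says.** - **Formula.** The entry "Renal Clearance [1] Single Dose" in SAP Table 7 (section 8.1.3.1) reads with its formula "Renal Clearance [1] Single Dose: CL r = A e /AUC inf". The repeat-dose formula in the same cell divides Ae over the dosing interval by AUC over that interval, so its windows match.
- **Numerator.** Ae is the "Cumulative amount of drug excreted in urine", the sum of concentration times volume over the urine collected. No extrapolation is defined.
- **Urine window.** Footnote 7 to the Part 1 schedule (Protocol 6.1.1, SAP 11.2.1.1) has urine "collected pre-dose and over the post-dose intervals 0-12 hours and 12-24 hours".
- **Time origin.** For divided doses, "Time 0 is the first dose and subsequent doses are per regimen (q1h, q4h or q16" hours). Cohort 8 was dosed at 0 h and 16 h (SAP 11.5.1), so only 8 h of urine follows its second dose.
- **Denominator.** The notes to SAP 11.3.1 state "All Subsequent draws after 2 hour will be at hours 4, 6, 8, 12, 18, 24, 36, 48, and 72 in Part 1"; Table 7 then adds the extrapolated tail.
- **Alternative already derived.** Table 7 lists AUC(0-24) for Part 1: "Area under the concentration-time curve from time zero to the time of the 24 hour concentration".
- **Scope.** Table 7 limits AUC to infinity to single-dose profiles in Part 1 and Day 1 of Part 2, and SAP 11.5.1 codes Cohort 8 as multiple-dose. SAP 8.1.3.2 nevertheless uses AUC to infinity for the Part 1 multiple-dosing treatments in the dose-proportionality analysis.

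**The concern.** If renal clearance is constant, the amount excreted up to 24 h equals CLr times AUC(0-24). Dividing it by AUC to infinity leaves out whatever is excreted after 24 h, so the mismatch can only lower CLr. The size depends on how long before 24 h the last dose was given, which differs between Part 1 regimens.

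CLr is a listed Part 1 secondary PK endpoint with no cohort excluded, and it is summarised by treatment. The Part 2 schedules show no urine PK collection, so Part 1 may supply the only CLr values in the study. What is at stake is the accuracy of a descriptive parameter, mainly in one cohort.

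**Working it through.** The documents give no figure for CLr, Ae or the share of AUC after 24 h, so there is nothing to reproduce.

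**Inputs.** Urine window 24 h from first dose (Protocol 6.1.1). Equal doses at 0 h; at 0 h and 4 h; hourly from 0 to 8 h; and at 0 h and 16 h (SAP 11.5.1). Half-life "1.5-3h observed versus 14.1h predicted" (Protocol 3.1.1), so 1.5-3 h is used. For absorption, ka = 1.4 per h is the protocol's predicted value (section 3.4.2) and is an assumption here.

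**Step 1: form of the bias.** With linear PK, Ae(0-24) = CLr x AUC(0-24). The Table 7 formula therefore returns CLr x (1 - f), where f is the fraction of AUC to infinity that falls after 24 h.

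**Step 2: f by superposition.** One compartment, k = ln 2 / half-life, doses at times t_i, s = 24 - t_i:
- (a) instantaneous input: f = mean of exp(-k s)
- (b) first-order input: f = mean of [ka exp(-k s) - k exp(-ka s)] / (ka - k)

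Examples for (a) at a 3 h half-life (k = 0.231):
- single dose: exp(-24k) = 0.0039
- 0h/16h: (0.0039 + exp(-8k)) / 2 = (0.0039 + 0.1575) / 2 = 0.0807

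At 1.5 h (k = 0.462), 0h/16h gives (0.00002 + 0.0248) / 2 = 0.0124.

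Underestimate of CLr (%):

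| Regimen | (a) 1.5 h | (a) 2 h | (a) 3 h | (b) 1.5 h | (b) 2 h | (b) 3 h |
|---|---|---|---|---|---|---|
| Single, 0h | 0.002 | 0.024 | 0.39 | 0.002 | 0.032 | 0.47 |
| 0h/4h | 0.006 | 0.061 | 0.69 | 0.008 | 0.081 | 0.82 |
| Hourly x 9 | 0.018 | 0.14 | 1.2 | 0.027 | 0.19 | 1.4 |
| 0h/16h | 1.2 | 3.1 | 8.1 | 1.9 | 4.2 | 9.7 |

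The result depends on half-life. At the superseded prediction of 14.1 h, variant (b) would give 32% for a single dose and 51% for 0h/16h.

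**Step 3: effect of matching the windows.** With AUC known exactly, Ae(0-24)/AUC(0-24) returns CLr in every regimen.

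**Step 4: effect on the printed plasma schedule.** Plasma is drawn at 12, 18 and 24 h, with none at 16 h, so the 12-18 h trapezoid spans Cohort 8's second dose. I applied linear-up/log-down trapezoids at the printed times to error-free concentrations, with half-life 1.5-3 h and ka 1.4 or 3 per h (both assumed). For Cohort 8, AUC(0-24) comes out about 5-11% too high. The two ends of the range are:
- half-life 3 h, ka 1.4: as written, (1 - 0.0967) / 1.096 = 0.824, or 17.6% low; after the change, 1 / 1.107 = 0.904, or 9.6% low
- half-life 1.5 h, ka 3: as written, (1 - 0.0147) / 1.0515 = 0.937, or 6.3% low; after the change, 1 / 1.052 = 0.950, or 5.0% low

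Overall, Cohort 8 CLr is about 6-18% low as written and still about 5-10% low with matched windows.

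**The case against.** **For true single doses there is practically nothing to correct.** A 24 h collection spans 24/3 = 8 to 24/1.5 = 16 half-lives. Trapezoid error on the printed schedule, about 0.6-1.6% for a single dose, exceeds the window bias. This stands. A reader might infer that single-dose CLr is materially wrong throughout Part 1; the observed half-life does not support that. For the 0h/4h and hourly regimens, too, trapezoid error outweighs the window bias, and it pushes CLr the other way.

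**The SAP does not say that the single-dose formula governs Cohort 8.** The cohort is coded multiple-dose, and Table 7 ties AUC to infinity to single-dose profiles. This stands as an ambiguity. Against it, SAP 8.1.3.2 uses AUC to infinity for these cohorts, and no other Part 1 CLr formula exists: the second is for repeat dosing, and AUC over the dosing interval is derived for Part 2 only. Either the first formula applies, or Cohort 8 has no defined CLr.

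**Nothing is decided on CLr.** A reader might infer that the plan would report a false difference between regimens. No such comparison is planned: CLr receives only median, maximum, minimum, mean and SD (SAP 8.1.3.1), enters no model, and is not in the minimum data set for dose escalation (Protocol 9.8.1). With 6 active subjects per cohort and an assumed between-subject CV of 20-30%, the standard error of a cohort mean is 20/√6 = 8% to 30/√6 = 12%, as large as the worst-case window bias. This stands and limits the importance of the point.

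**The collection window is not fixed.** Urine timing may be altered (Protocol 6.4.2), urine assay is subject to feasibility (6.4.3), and CLr is reported only as data permit. Those conditions govern whether CLr is obtained; they do not make the two windows in the formula agree.

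**Conclusion.** The mismatch is real and minor. As scheduled, the Part 1 formula has a 24 h numerator and an unlimited denominator, and the effect of that mismatch is downward in every regimen. At a half-life of 1.5-3 h it is under 0.5% for single doses, at most about 1.4% for 0h/4h and hourly x 9, and about 1-10% for 0h/16h if the formula is used there. These sizes assume linear one-compartment kinetics, constant renal clearance and no slower terminal phase.

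A reader might also infer that matching the windows makes Cohort 8 CLr unbiased. That holds only if AUC is known exactly; the printed sampling times do not allow it.

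**What to change.** In SAP Table 7, define Part 1 CLr = Ae(0-24)/AUC(0-24), label the numerator Ae(0-24), and state that it applies to all Part 1 regimens, divided-dose cohorts included, with time counted from the first dose. If urine collection was extended beyond 24 h for any cohort, use the AUC over the same interval. Add a note to the CLr summary that Cohort 8 values carry AUC error because no plasma sample is scheduled at 16 h.

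The cost is one formula and one footnote. No new samples are needed, AUC(0-24) is already a Part 1 parameter, and CLr no longer depends on estimating the terminal slope. The change also settles which formula applies to the divided-dose cohorts.
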